# 5.3 Assessment of inclusion criteria

All patients will, prior to inclusion, have went through standard clinical work-up and have been seen in the outpatient clinic by a gastroenterologist. They have been examined and have taken blood samples to exclude competing diseases affecting the GI system. Colonoscopy will have been performed on clinical indication.

#### 5.4 Trial termination, discontinuation, and replacements of patients

The investigation is terminated when 20 patients have completed the two intervention periods, or if investigators become aware of any conditions or events that suggest a possible hazard to the patients. Premature termination may also be a result of failure to recruit a sufficient number of patients. The trial is terminated when the data are analysed.

Participants will be discontinued if she/he withdraws her/his consent, in case of pregnancy, or intestinal surgery. Dropouts will be attempted replaced, until at least 20 participants have completed all three intervention periods. This can ensure a balanced number of patients receiving treatment. No more than 40 patients will be included in the trial, in the attempt to find 20 patients who, complete both intervention periods.

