# 2.3 Hypotheses

## 2.3.1 Primary H0

1. Oral intake of FMT capsules is safe and well tolerated in patients with DM1, including those with prolonged gastric emptying and small intestinal transit.

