# 6.0 Risks, adverse events, and nuisance

We expect no long-term risks following participation. Side effects of FMT tend to be mild and short-lasting. Treatment with FMT is generally well tolerated, but specific side effects are sparsely elucidated. Experience has shown that about one-third of patients receiving FMT experience transient diarrhea, nausea or bloating(16, 33, 34). Less than 1 in 10 experience fever and discomfort in the hours after FMT. For most patients, the condition lasts less than a day and does not require treatment. The patient is carefully instructed after each treatment and receives information of how to contact the department in case of worsening or side effects. Approximately 1 in 20 develops symptoms compatible with bacterial overgrowth. These are treated according to local instructions of the department. Less than 1% of the patients receiving FMT experience severe long-term symptoms of infection with infectious disease from the donor. The risk is reduced as much as possible by thorough selection and screening of donors and donor faeces on accordance with tissue standards and the European Union Tissue and Cells Directives which leads to the safety standards comparable to handling of blood components. The application form of capsule FMT is minimally invasive. The inconvenience is ingestion of the many capsules and overnight fasting prior to ingestion of the capsules. Treatment with peristalsis-promoting medication helps in addition to accelerated emptying of the stomach for possible nausea.

Blood sampling may be associated with minor discomfort, bleeding, hematoma, and/or bruising, and there is a minimal risk of infection or inflammation, however this is easily treated. There are no known risks involved with faecal sampling.

The wireless Motility Capsule is a noninvasive and painless method of obtaining important data of the GI tract. We anticipate no adverse events (AE) caused by the Wireless Motility Capsule, however, there is a low risk of retention of the capsule. If a patient does not pass the capsule within 4 weeks, they will be offered an abdominal x-ray and possibly gastroscopic, colonoscopic or surgical removal of the capsule.

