## 6.1.1 Adverse events

Adverse events are defined according to the ICH Harmonized Tripartite Guide to Good Clinical Practice (https://www.ema.europa.eu/en/documents/scientific-guideline/ich-e-6-r2-guideline-good-clinical-practice-step-5\_en.pdf).

- Adverse Event (AE): any untoward medical occurrence in a patient which does not necessarily have a causal relationship with the trial
- Adverse reaction (AR): any adverse and undesirable reaction to the experimental treatment, regardless of dose.
- Unexpected adverse reaction (UAR): a side effect whose nature or severity does not match the expected side effects of the trial.
- Serious Adverse Event (SAE) or serious adverse reaction (SAR): any adverse event or adverse reaction that results in:
  - 1. death or
  - 2. a serious deterioration in health that
    - resulted in life-threatening illness or injury
    - resulted in permanent impairment of body structure or body function
    - required hospitalisation or prolongation of existing hospitalisation
    - resulted in medical or surgical treatment to prevent the above

- foetal death, congenital anomaly or birth defect or any other negative effect on the foetus.

- Suspected Unexpected Serious Adverse Reaction (SUSAR): a suspected but unexpected serious adverse reaction that has not been previously described for the treatment with FMT according to published science.

All patients with expected or unexpected events or side effects are offered admission to the treatment ward if necessary. Furthermore, all unexpected side effects and AE will be reported in the "Adverse Event CRF" containing following information:

1. Degree of difficulty (mild, medium, severe)

- 2. Relation to the investigation (expected/unexpected)
- 3. Duration (start date, end date, are the condition persistent after the last examination)
- 4. The graduation of the adverse event according to the CTCAE v0.5

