The connection to the study ends when a participant has completed the second intervention period, after approximately 12 weeks, or withdraws her/his consent. The patient may be followed up after the trial if an AE/SAE related to the study is not resolved when the intervention ends. In that case, the patient will be offered to be followed up by telephone until a solution is found or until it terminates.

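### Section 5.4 does not separate stopping treatment from leaving the study, and plans no assessments after stopping beyond optional follow-up of unresolved related events, while dropouts are replaced

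*Protocol*

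**What the plan says.** Protocol 5.4 gives the rule for individual patients: "Participants will be discontinued if she/he withdraws her/his consent, in case of pregnancy, or intestinal surgery". It then deals with replacement: "Dropouts will be attempted replaced, until at least 20 participants have completed all three intervention periods". The cap follows: "No more than 40 patients will be included in the trial, in the attempt to find 20 patients who, complete both intervention periods".

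Protocol 6.1.1.1 says when participation ends: "The connection to the study ends when a participant has completed the second intervention period, after approximately 12 weeks, or withdraws her/his consent". It adds one form of later contact: "The patient may be followed up after the trial if an AE/SAE related to the study is not resolved when the intervention ends". The same section has events entered in the case report form at clinical attendances or at the telephone call one week after each intervention.

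Four other places bear on the point:

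- Section 2.3.1 makes tolerability part of the primary hypothesis: "Oral intake of FMT capsules is safe and well tolerated in patients with DM1".
- Section 2.4.2 lists adverse events in weeks 5-8, serious events in long-term follow-up, and questionnaires at weeks 4, 8 and 26 as secondary endpoints.
- Section 6.1.1 includes in its definition of a serious event "foetal death, congenital anomaly or birth defect or any other negative effect on the foetus".
- Section 9.0 ends data collection after withdrawn consent only where the participant objects to it.

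**The concern.** A patient who took the first dose badly and does not want the second fits none of the three reasons in 5.4 except withdrawn consent, and 6.1.1.1 ends the connection to the study at that point. Pregnancy and intestinal surgery can themselves matter for safety, yet 5.4 treats them only as reasons to discontinue. In all three cases the protocol is silent on which visits, calls and questionnaires continue, and the patient is replaced.

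In a trial meant to establish tolerability, stopping because of side effects is itself a tolerability result. As written, the protocol asks for no reason for stopping and schedules nothing afterwards. If FMT causes the side effects, refusals of the second dose would be expected more often in the arm that received FMT first. The later comparisons, including two doses against one, would then lose patients unevenly. An analysis plan can choose its populations, but it cannot recover data that were never collected.

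**Working it through.** The protocol gives no dropout rate and no power calculation (4.1), so there is no figure to reproduce. The check is a reading of the schedule, followed by simple arithmetic for scale.

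**Step 1. What a patient who declines the second dose would still contribute** (2.4, Table 1, 3.6.4 to 3.6.7)

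| Data | When | Planned if the second dose is declined? |
|---|---|---|
| Primary endpoint | First week after visit 4 (week 1) | Yes, already collected |
| Week-4 questionnaires, motility capsule, CT, breath test, stool, blood | Visits 5 and 6, week 5 (+1) | Yes, they come before visit 7 |
| Second diary, side-effect report and one-week call | Week after visit 7, week 6 (+2) | No, tied to the second dose |
| Week-8 questionnaires, motility capsule, stool, blood | Visit 8, week 10 (+2) | Not stated to continue |
| Week-26 diary and questionnaires, long-term serious events | Week 26 and later | Not stated to continue |

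A patient discontinued for pregnancy or surgery before the second dose loses the same last three rows. Week-4 data would be lost only if the patient left or was discontinued before visits 5 and 6.

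**Step 2. Whether other text fills the gap**

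- Follow-up under 6.1.1.1 is optional and limited to an event already judged related and still unresolved. It does not cover new events, questionnaires or samples.
- Section 9.0 permits further collection after withdrawal unless the patient objects, but schedules none. It also sits badly with 6.1.1.1, which ends the connection at withdrawal.
- The two-monthly calls in 3.6.8 are for patients who have completed the study period, and are optional.
- Section 3.2.1 foresees patients who could not easily swallow the capsules or who vomited, but provides for them only after both treatments are completed.
- No section follows a pregnancy to its outcome, so the foetal part of the serious-event definition has no planned source of data.

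**Step 3. When participation ends**

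- Section 6.1.1.1 puts the end at about 12 weeks; 2.4.2 requires data at week 26 and long-term serious events.
- Section 5.4 speaks of two, three and both intervention periods; 3.1 describes two.

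**Step 4. Scale**

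Let k be the number of patients who stop and are replaced. The share of enrolled patients without the later data is k/(20 + k). The values of k are assumptions; only the last is fixed by the cap (40 - 20 = 20).

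| k | Share |
|---|---|
| 2 | 2/22 = 9% |
| 5 | 5/25 = 20% |
| 10 | 10/30 = 33% |
| 20 | 20/40 = 50% |

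If no late serious event were seen in the 20 completers, the number of enrolled patients with such an event could still lie anywhere from 0 to k. For k = 2 that is 0% to 9%, and for k = 5 it is 0% to 20%.

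**The case against.** The strongest reply is that each intervention is a single supervised capsule session, so there is no continuing treatment to stop during the placebo-controlled period. Visits 5 and 6 come before the second dose, and the primary endpoint closes a week after the first. Both points stand. A reader might infer that the week-4 comparison sets FMT tolerators against nearly all placebo patients; the schedule does not support that.

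Three other stronger readings also fail:

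- **That stopping is possible only for the three listed reasons, and that intolerance is recorded as lost consent.** Section 5.4 does not call its list exhaustive, and no section prescribes that coding. It is a likely result of the list, not a stated rule.
- **That there is no follow-up, or that outcomes of stopping are never collected.** Sections 6.1.1.1 and 9.0 leave some room, and adverse events are entered in the case report form while the patient attends.
- **That 5.4 and 6.1.1.1 flatly contradict each other on pregnancy and surgery.** One speaks of discontinuation, the other of the connection to the study. The second could mean that these patients stay connected, which is a reason to state it.

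The surgical example needs restraint too. Section 6.0 mentions "possibly gastroscopic, colonoscopic or surgical removal of the capsule", but surgery is only one option and need not be intestinal. Section 6.1.1.3 reports 20 retentions in nearly 6000 patients, none needing surgery. Pregnancy is an exclusion criterion and is tested for at visit 2 where relevant, so cases should be few. The one third of FMT recipients with transient symptoms in 6.0 is not a stopping rate. Finally, 4.2 leaves analysis populations to the analysis plan, so a completers-only analysis cannot be presumed.

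What remains is that the protocol plans no scheduled assessment after stopping, and that patients who stop are replaced.

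**Conclusion.** The point holds in a limited form. The data at risk are adverse events in weeks 5-8, long-term serious events, week-8 and week-26 outcomes, and foetal outcomes. The primary endpoint and the week-4 comparison are largely safe.

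The size depends on how many patients stop, which the protocol does not estimate: 9% of those enrolled for 2 replaced patients, 20% for 5, and 50% at the cap. With the 10 patients per arm shown in Figure 1, one patient is 10% of an arm.

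The conclusion assumes that sites follow 5.4 and 6.1.1.1 as written and do not keep stopped patients in follow-up on their own initiative. It does not depend on the analysis populations chosen later. It is a correction worth making because it is cheap and because missed follow-up cannot be recovered afterwards.

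**What to change.** Amend 5.4 and 6.1.1.1 to define two states:

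1. *Treatment discontinuation*: the next dose is not taken, for whatever reason. The remaining calls, questionnaires and event recording continue at their planned times, with the second one-week call set by calendar time if there is no second dose. The reason is coded, with adverse event as one of the options.
2. *Study withdrawal*: only when the patient refuses further data collection, in line with 9.0. Data collected up to then are kept.

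State also that the data of replaced patients are kept, and that the outcome of any pregnancy is collected as safety data. Reconcile 2.4.2, 5.4, 6.1.1.1 and 9.0 on when participation ends (about 12 weeks against week 26) and on the number of intervention periods in 5.4.

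The cost is a short protocol amendment, one case report form field, and a few extra contacts with patients who have stopped. No clinical stopping rule is proposed; whether and when a patient should receive another dose is outside this point.

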# 6.0 Risks, adverse events, and nuisance

We expect no long-term risks following participation. Side effects of FMT tend to be mild and short-lasting. Treatment with FMT is generally well tolerated, but specific side effects are sparsely elucidated. Experience has shown that about one-third of patients receiving FMT experience transient diarrhea, nausea or bloating(16, 33, 34). Less than 1 in 10 experience fever and discomfort in the hours after FMT. For most patients, the condition lasts less than a day and does not require treatment. The patient is carefully instructed after each treatment and receives information of how to contact the department in case of worsening or side effects. Approximately 1 in 20 develops symptoms compatible with bacterial overgrowth. These are treated according to local instructions of the department. Less than 1% of the patients receiving FMT experience severe long-term symptoms of infection with infectious disease from the donor. The risk is reduced as much as possible by thorough selection and screening of donors and donor faeces on accordance with tissue standards and the European Union Tissue and Cells Directives which leads to the safety standards comparable to handling of blood components. The application form of capsule FMT is minimally invasive. The inconvenience is ingestion of the many capsules and overnight fasting prior to ingestion of the capsules. Treatment with peristalsis-promoting medication helps in addition to accelerated emptying of the stomach for possible nausea.

Blood sampling may be associated with minor discomfort, bleeding, hematoma, and/or bruising, and there is a minimal risk of infection or inflammation, however this is easily treated. There are no known risks involved with faecal sampling.

The wireless Motility Capsule is a noninvasive and painless method of obtaining important data of the GI tract. We anticipate no adverse events (AE) caused by the Wireless Motility Capsule, however, there is a low risk of retention of the capsule. If a patient does not pass the capsule within 4 weeks, they will be offered an abdominal x-ray and possibly gastroscopic, colonoscopic or surgical removal of the capsule.

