## 3.6.7 Investigations after 2. Intervention I (visit 8)

After an additional 4 weeks since the second intervention, investigations will be repeated once again except for the breath test and low-dose CT scan.

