#### 6.1.1.3 Wireless Motility Capsule

The WMC is an orally ingested data recording device that enables simultaneous assessment of regional and whole gut transit. The WMC is CE marked and approved by the US Food and Drug Administration for evaluation of patients with suspected delayed gastric emptying and evaluation of colonic transit time in patients with chronic constipation. The WMC is contraindicated to patients with a history of gastric bezoar, swallowing disorders, dysphagia to food or pills, suspected

stricture or fistulae along the GI tract, physiological GI obstruction, GI surgery within the previous 3 months, Crohn's disease, diverticulitis or an implanted or portal electromechanical medical device(31).

The most serious AEs associated with the WMC are the inability to confirm passage of the capsule outside the body, capsule retention and obstruction. In a previous trial with nearly 6000 patients receiving WMC there were 20 reports of prolonged capsule retention (5 in the stomach, 2 in the small intestine and 13 in the colon) which yield a retention rate of 0,33%(30). An upper endoscopy was required for extraction of the 5 capsules that were retained in the stomach. Of the remaining 15 cases, only 1 capsule required drug intervention. The other 14 capsules passed spontaneously. None of the patients required surgical intervention. If it cannot be confirmed that the capsule has passed five days after ingestion the manufacturer's follow-up recommendations should be followed. This is based on the location of the capsule which is determined by the pH profile obtained during the study. If the pH profile suggests that the capsule is retained in the stomach or bowel. Due to the low risk of obstruction once the capsule is in the colon, no specific follow-up is necessary if the capsule is retained in this area.

Other side effects associated with WMC include abdominal pain, dysphagia, nausea and diarrhea. However, as many of the patients had these symptoms at baseline, these side effects have been difficult to determine if they were caused by the WMC. Patients are provided information about the risks in the participants information sheet, which they are urged to read comprehensively prior to consenting to participate.

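### Sections 6.0 and 6.1.1.3 give unreconciled rules for a retained motility capsule, and the visit 8 capsule has no stated passage check at either time point

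*Protocol*

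**What the plan says.** **Rule in section 6.0.** "If a patient does not pass the capsule within 4 weeks, they will be offered an abdominal x-ray". Taking the capsule out by endoscopy (upper or lower) or by an operation is named as a further possibility. Location plays no part in this rule.

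**Rule in section 6.1.1.3.** "If it cannot be confirmed that the capsule has passed five days after ingestion the manufacturer's follow-up recommendations should be followed". Location is to be read from the pH profile. The next sentence is "If the pH profile suggests that the capsule is retained in the stomach or bowel", and it stops there, with no action attached. For a capsule in the colon, the section says that "no specific follow-up is necessary if the capsule is retained in this area".

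Neither section refers to the other.

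**Capsule schedule.** Section 2.4.2 and Table 1 give three capsules per patient, at visits 2, 5 and 8. Section 3.6.7 says that at visit 8 "investigations will be repeated once again except for the breath test and low-dose CT scan", so the motility capsule stays in. Visit 8 is at week 10 (+2) and is the last column of Table 1.

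**End of participation.** Section 6.1.1.1 says: "The connection to the study ends when a participant has completed the second intervention period, after approximately 12 weeks". Figure 1 labels the evaluation after the second intervention as end of study. The same section has adverse events recorded at clinic attendances or at the call one week after each intervention. None of these contacts is scheduled after visit 8.

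**The concern.** Staff who hold this protocol have two instructions for the same event, and for a capsule in the colon the instructions differ in substance. One offers imaging and possible colonoscopic removal; the other asks for nothing specific. Retention is a risk that the protocol itself names, and section 6.1.1.3 places retention and obstruction among the most serious events linked to the device.

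The schedule adds a second problem. The last capsule is swallowed at the last scheduled visit, so whichever time point applies, it comes when no study contact is planned. At stake is the follow-up of a known device risk, and the completeness of the adverse event record in a trial whose main purpose is safety.

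**Working it through.** **1. The two rules side by side**

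| | Section 6.0 | Section 6.1.1.3 |
|---|---|---|
| Trigger | not passed at 4 weeks | passage unconfirmed at five days |
| Depends on location | no | yes, by pH profile |
| Stomach or bowel | x-ray, possible removal | manufacturer's advice; own sentence has no action |
| Colon | x-ray, possible removal, colonoscopy included | nothing specific needed |

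The trigger row can be read as two stages. The colon row cannot be reconciled that way without further text.

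**2. The protocol's own retention figure (section 6.1.1.3)**

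By site: 5 stomach + 2 small intestine + 13 colon = 20. By outcome: 5 upper endoscopy + 1 drug treatment + 14 spontaneous passage = 20. Rate: 20 / 6000 = 0.333%, which reproduces the stated 0.33%. Colonic share: 13 / 20 = 65%.

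**3. Timeline, in Table 1 week labels with the windows**

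| Capsule | Swallowed | Five-day point | 4-week point | Next study dose |
|---|---|---|---|---|
| 1 (visit 2) | week -2 to -1 | about -1.3 to -0.3 | 2 to 3 | week 1 |
| 2 (visit 5) | week 5 to 6 | about 5.7 to 6.7 | 9 to 10 | week 6 to 8 |
| 3 (visit 8) | week 10 to 12 | about 10.7 to 12.7 | 14 to 16 | none |

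For capsule 3 both points lie after the last scheduled visit. Counted from week -3 with no week 0, visit 8 at week 10 is 12 weeks after inclusion, which matches the stated length of participation. Read as a week label instead, 12 is still earlier than 14. The 4-week point is therefore after the end of participation on either count.

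**4. Expected number of retentions**

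With p = 20/6000 = 1/300 and independent ingestions, the expected number is n × p and the chance of at least one is 1 − (1 − p)^n.

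- All capsules in 20 completers: n = 20 × 3 = 60. Expected 60/300 = 0.20; chance 1 − (299/300)^60 = 18.2%.
- Third capsules only: n = 20. Expected 20/300 = 0.07; chance 1 − (299/300)^20 = 6.5%.
- Upper bound: section 5.4 allows 40 inclusions to find 20 completers. If the other 20 leave before visit 8, they take at most two capsules each: n = 60 + 40 = 100. Expected 0.33; chance 1 − (299/300)^100 = 28%.
- Retentions needing upper endoscopy, at 5/6000 per ingestion: 60 × 5/6000 = 0.05 in all, and 20 × 5/6000 = 0.017 for the third capsule.

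**5. Reach into the primary endpoint**

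The primary endpoint covers the week after the first dose (section 2.4.1). Only capsule 1 comes before it: 20 × 1/300 = 0.07 expected retentions, with the same capsule exposure in both arms.

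**The case against.** The strongest defence is that the sections describe two stages: locate the capsule at five days, then offer an x-ray at 4 weeks if it is still there. That is a fair reading of the time points, but the protocol does not state it, and it leaves the colon unresolved. The unfinished stomach-or-bowel sentence may be only a drafting slip; the colon conflict does not depend on it.

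The second defence is that the third capsule is not ignored. The patient wears a receiver until the capsule leaves the body (section 3.3.2), and colonic transit time is an endpoint after each intervention period. Section 2.4.2 has a week-26 follow-up and counts serious adverse events over the long term. Sections 3.1 and 3.6.8 describe two-monthly calls, which patients may refuse. Section 6.1.1.1 permits telephone follow-up of an unresolved study-related event. Any of these might reveal a retention. None is a stated check of passage at five days or 4 weeks after visit 8. Sections 3.6 and 11.0 count ten and nine visits against eight in Table 1, but neither describes a visit after visit 8.

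A reader might infer more than the documents support:

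- **That both doses are given before anyone looks for retention.** This follows only if the five-day rule is set aside. At nominal timing, the five-day point precedes the next dose for capsules 1 and 2; only an unfavourable use of the windows for capsule 2 reverses this.
- **That the trial selects patients for slow transit.** Section 5.1 selects on diabetes duration and symptom score. The 65% and 58% with prolonged gastric emptying and colonic transit in section 3.3.2 come from a cited study, and the capsule is there to classify patients as normal or prolonged.
- **That section 6.0 denies any capsule risk.** The sentence that anticipates no events goes on to name a low risk of retention.

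**Conclusion.** The point holds as a contradiction on participant safety and a gap in scheduled follow-up. The two sections conflict directly on colonic capsules, the site of 13 of the 20 retentions that the protocol cites, and they leave the relation between five days and 4 weeks unstated. For the visit 8 capsule, no contact is scheduled at either time point, and the later one falls after participation ends.

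The expected number of events is small: 0.20 retentions in 60 ingestions (18% chance of at least one), of which 0.07 (6%) come from the third capsules. These figures assume independent ingestions at the protocol's general rate of 0.33%. The documents give no rate for this population; the expected counts would scale in proportion to it. Most cited retentions ended without intervention (14 of 20), and none needed surgery.

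It would go too far to say that the primary endpoint is compromised. It is untouched by the second and third capsules, and the first contributes about 0.07 expected retentions under equal exposure in both arms, so the effect is likely negligible. The case for correction rests on conflicting instructions for a named risk, which are cheap to put right.

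**What to change.** 1. Reconcile sections 6.0 and 6.1.1.3 into one consistent statement covering the time point or points, the treatment of each location including the colon, and the unfinished stomach-or-bowel sentence. Which rule applies is for the sponsor to decide.
2. State how passage, or retention, of the visit 8 capsule is captured and recorded, given the end of participation set in section 6.1.1.1.
3. Record passage status and date in the eCRF for each of the three capsules, taken from the recording that is already made.

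The cost is a protocol amendment, one eCRF field completed per capsule, and possibly one telephone contact after visit 8. No new investigation is needed to record passage, and no endpoint changes.
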